primarily to genotype – a known confounder (41). The American College of Sports Medicine’s classifications of training status (i.e., <150 minutes of moderate-intensity and/or <75 minutes of vigorous aerobic exercise per week for the last 3 months) as well as normative $\text{VO}_{2\text{max}}$ values will be used to dichotomize the groups with the fit (and chronically-trained) and unfit (and sedentary) group having values in the upper and lower quartiles (i.e., $\geq 75^{\text{th}}$ percentile and $\leq 25^{\text{th}}$ percentile) for their age and sex, respectively (42). This equates to a $\text{VO}_{2\text{max}}$ value of ≥ 55.2 and 44.7 ml/kg/min for fit males and females, respectively, and ≤ 40.1 and 30.5 ml/kg/min for unfit males and females, respectively. Participants will then be provided with a wearable, wrist-worn sleep and cardio-autonomic function monitor, to be worn on the non-dominant wrist throughout the entirety of the project timeline, including a two-week initialization period to establish baseline sleep cardio-autonomic data. This initialization period will take place following consent and prior to the first data collection visit. Next, participants will then be familiarized with daily sleep, physical activity, and 3-day nutrition logs as well as a PVT smart phone application, all of which will be performed throughout the study. Lastly, participants will be assessed for sleep chronotype via a morningness-eveningness questionnaire to inform any potential differences in sleep intervention response post hoc. Following the initialization period, participants will be randomly assigned to either a normal or partial sleep deprivation intervention, both of which will last 4 days. The partial sleep deprivation intervention will consist of prescribed bed and wake times eliciting a 30% reduction in habitual time in bed, identical to a protocol utilized by Roberts, et al. (43). Following the first sleep intervention period, participants will again report to the ISSM for the first of four data collection visits (i.e., Post-Test 1). Data collection will consist of assessment of central hemodynamics, cardio-autonomic function, physical and cognitive performance, as well as overall health. Participants will then undergo a 7-day washout/ post-intervention observation period, in which they will continue to track and log their sleep and perform daily PVT to allow for recovery evaluation in those metrics, prior to crossing over to the other sleep intervention. During the washout period, participants will also return to the lab to repeat the blood work and CMJ testing to allow for recovery assessment in those values (i.e., immediate post-intervention vs 3-day post-intervention values; Recovery 1). Following completion of the washout/observation period, participants will crossover to the other sleep intervention and repeat the testing protocols (i.e., Post-Test and Recovery 2). Data collection visits will occur at the same approximate time of day for each individual to account for diurnal patterns in the data collected. In total, the protocol will last approximately 5 weeks and consist of 5 visits.

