Experimental Visits: Following the first sleep intervention period, participants will come in for the first of four data collection visits (i.e., Post-Test 1). Data collection visits will begin of the completion of the Pittsburgh Sleep Quality Index (PSQI) and Profile of Mood States (POMS) questionnaire to characterize sleep quality and psychological mood states, respectively. Next, central arterial pulse wave form analysis and pulse transit time (carotid-femoral PWV [cf-PWV]; via applanation tonometry) will be assessed using a SphygmoCor XCEL device (AtCor Medical, New South Wales, Australia), followed by a standard venipuncture procedure to allow for inflammatory marker characterization, total blood cell counting, as well as blood lipid and glucose profiling to account for known hemodynamic confounders (26). The venipuncture procedure will be performed by the primary investigator (certified phlebotomist trained; 5+ years of experience) following the attached standard operating procedure for venipuncture and will entail the collection of 10-30 mL of blood, as is typical of a standard blood venipuncture procedure. If the primary investigator is unavailable to perform the procedure or is unable to do so, the Clinical Research and Trials Unit will be utilized. Lastly, participants will perform a short countermovement jump (CMJ) test to quantify their reactive strength index (RSI).

Participants will then undergo a 7-day washout/ post-intervention observation period, in which they will continue to track and log their sleep and perform daily PVT to allow for recovery evaluation in those metrics, prior to crossing over to the other sleep intervention. During the washout period, participants will also return to the lab to repeat the blood work and CMJ testing to allow for recovery assessment in those values (i.e., immediate post-intervention vs 3-day post-intervention values; Recovery 1). Following completion of the washout/observation period, participants will be assigned to the other sleep intervention in a crossover fashion and complete the second 4-day intervention before returning for another data collection visit (i.e., Post Test 2) identical to Post Test 1. They will then enter another 7-day post-intervention observation period and performing a second recovery data collection visit (i.e., Recovery 2). Data collection visits will occur at the same

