approximate time of day for each individual to account for diurnal patterns in the data collected. In total, the protocol will last approximately 5 weeks and consist of 5 visits.

Central Hemodynamic Assessment: Participants will be assessed for central arterial pulse wave form and cf-PWV following both sleep interventions with re-analysis occurring 3 days later to quantify the response to, and recovery from, the two sleep interventions between the two groups. The central hemodynamic (i.e., central blood pressure, augmentation index [absolute and relative to a heart rate of 75 beats per minute], mean arterial pressure, and pulse pressure) and arterial stiffness (i.e., cf-PWV) variables of interest will be collected and analyzed following methods identical to those utilized by Grosicki, et al. (34).

Health and Well-Being Assessment: Both metrics of sleep quality and cardio-autonomic function (i.e., resting heart rate, heart rate variability, and a proprietary, WHOOP-generated recovery score) will be collected via the WHOOP devices. The wearing of the device throughout the entirety of the project timeline will allow for the quantification of these measures in response to, and recovery from, the two sleep interventions, which will be compared between the two groups. Further, data from the devices will be analyzed following protocols set forth by Greenwalt, et al. (44). Using blood samples collected during the venipuncture protocols performed at the four data collection visits, sleep intervention response and recovery levels of circulating plasma concentrations of pro- (CRP, IL-6, IL-1 β , and TNF- α) and anti-inflammatory (IL-10) cytokines will be assessed using protocols similar to that outlined by Smith, et al. (45). Additionally, portions of the blood samples will undergo hematologic analysis to characterize shifts in the composition of immune cells through methods similar to those of Schluter et al. (46). Finally, POMS data will be used to evaluate intervention-associated shifts in psychological mood states between the two groups following the methodology of Shacham (47).

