16.2 N/A

17.0 Data Management and Confidentiality

17.1

Sample Size Estimation

Sample size requirements were determined via a priori power analyses using G*Power software (Ver. 3.1.9.4; Heinrich-Heine-Universität Düsseldorf, Düsseldorf, Germany) to ensure sufficient statistical power. To inform the expected effect size, we referenced Sunbul, et al. (49) who reported significantly higher wave velocity (PWV) values (5.33 ± 0.46 m/s) following one night of total sleep deprivation compared to one night of normal sleep (5.15 ± 0.26 m/s; $p=0.001$) in young, healthy males and females. Acknowledging that this will consist of an acute partial sleep deprivation intervention, a Cohen's f value of 0.24 was used in conjunction with an α level of 0.05, power of 0.80, with 2 groups (crossover design; 4 measures each), and a conservative correlation among repeated measured of 0.5. This resulted in a sample size estimate of 24 participants. The planned sample size was then increased based on the differences between the current study, the previous work, and the assessment of several secondary outcomes, as well as to account for expected attrition (~20%). Therefore, 30 participants will be recruited to maximize statistical power and account for expected attrition.

Statistics

Data will be presented as means \pm SD if normally distributed and assessed for normality via a Shapiro-Wilk Test. Assuming normality, all variables will undergo null-hypothesis testing with the α level set to 0.05. In the case that normality is violated, the appropriate non-parametric alternatives will be utilized. Analyses will be conducted using SPSS version 29.0 (SPSS, Inc., Chicago, IL).

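### The protocol contradicts itself on whether central hemodynamics are measured at the recovery visits, and the four measures in the sample size calculation depend on the answer

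*Combined protocol and SAP*

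**What the plan says.** Section 6.2, Central Hemodynamic Assessment, plans central pulse wave analysis together with "cf-PWV following both sleep interventions with re-analysis occurring 3 days later to quantify the response to, and recovery from, the two sleep interventions". That places tonometry at Recovery 1 and Recovery 2 as well as at the two Post-Tests.

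Section 6.2, Experimental Visits, describes the first recovery visit differently: "participants will also return to the lab to repeat the blood work and CMJ testing to allow for recovery assessment in those values". Section 6.1 says the same: "return to the lab to repeat the blood work and CMJ testing to allow for recovery assessment in those values". Recovery 2 is named, but its procedures are not listed.

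Other text in the same sections points towards wider collection. Experimental Visits opens by saying "participants will come in for the first of four data collection visits (i.e., Post-Test 1", and continues "Data collection visits will begin of the completion of the Pittsburgh Sleep Quality Index (PSQI". It then lists the mood questionnaire, pulse wave analysis with cf-PWV, venipuncture and the jump test, without confining the list to Post-Tests. Section 6.1, after introducing Post-Test 1, says "Data collection will consist of assessment of central hemodynamics, cardio-autonomic function, physical and cognitive performance, as well as overall health".

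Section 17.1, Sample Size Estimation, takes its effect size from a published PWV comparison and assumes "2 groups (crossover design; 4 measures each". Section 17.1, Analysis of Variance, describes the cf-PWV hypothesis test with two assessments, one after normal sleep and one after restricted sleep.

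**The concern.** Central hemodynamics is the primary objective and Aim 1. One paragraph requires a second measurement three days after each intervention. The two paragraphs that say what happens at that visit leave it out, and they tie recovery to the blood and jump values only. These statements cannot all be followed.

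A team working from the visit description would not do tonometry at recovery, and a three-day value that is not taken then cannot be obtained later. If practice varied between staff or over time, recovery values would be missing unevenly across participants. The protocol would then state a hemodynamic recovery purpose with partial data or none behind it.

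The stated power is also involved. The sample size rests on PWV with four measures per participant. The four data collection visits supply four cf-PWV values only if tonometry is done at both recovery visits.

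**Working it through.** **1. The texts side by side**

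| Place | Tonometry at recovery? |
|---|---|
| 6.2 Central Hemodynamic Assessment | Yes, 3 days after each intervention |
| 6.1 overview, Recovery 1 | Not listed (blood and jump test only) |
| 6.2 Experimental Visits, Recovery 1 | Not listed (blood and jump test only) |
| 6.2 Experimental Visits, Recovery 2 | Not itemised |
| 6.2 Experimental Visits, general list | Yes, if the list covers all four visits |
| Figure 1 | Not visible in the text reviewed |

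If the general list governs all four visits, the restricted description of Recovery 1 is wrong. If the restricted description governs, the three-day clause is wrong. Reading the word re-analysis as reprocessing of old recordings does not help, because recovery at day 3 cannot be quantified without a new recording.

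**2. Measurements exposed**

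Planned per participant: 2 Post-Test + 2 recovery = 4. At 30 completers: 30 × 4 = 120 planned, of which 30 × 2 = 60 are recovery values. At 24 completers: 96 and 48. These are upper limits, reached only if every recovery measurement is skipped.

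**3. Reproducing the plan's sample size**

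Inputs from section 17.1: PWV 5.33 ± 0.46 against 5.15 ± 0.26 m/s; f = 0.24; α = 0.05; power 0.80; k = 2 groups; m = 4 measures; correlation ρ = 0.5; stated N = 24; attrition about 20%.

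- Effect size: d = (5.33 − 5.15) / √((0.46² + 0.26²)/2) = 0.18 / 0.374 = 0.48, so f = d/2 = 0.24. This matches.
- Within-between interaction, sphericity assumed: λ = f²·N·m/(1 − ρ), df1 = (k − 1)(m − 1), df2 = (N − k)(m − 1); power from the noncentral F distribution.
- At N = 24, m = 4: λ = 0.0576 × 24 × 4 / 0.5 = 11.06, df = 3 and 66, power 0.78. Power first exceeds 0.80 at N = 26 (0.82). The stated 24 is reproduced to within two participants.
- Attrition: 24 / (1 − 0.20) = 30. This matches.

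**4. The same calculation with two measures**

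| N | m = 4: λ | m = 4: power | m = 2: λ | m = 2: power |
|---|---|---|---|---|
| 24 | 11.06 | 0.78 | 5.53 | 0.61 |
| 30 | 13.82 | 0.88 | 6.91 | 0.72 |

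With two measures, N = 36 gives just under 0.80, and N = 38 is the first even total to exceed it (0.82).

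The two-measure result depends on ρ. With assumed values of 0.3 and 0.7, power at N = 24 is 0.48 and 0.83. Holding f at 0.24 for both m = 2 and m = 4 is a simplification.

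**The case against.** A reader might infer that the recovery hemodynamic data will simply not be collected. The documents do not support that. The Central Hemodynamic Assessment paragraph is itself an instruction specific to this outcome, and nothing ranks the visit summary above it. The general description of the data collection visits includes cf-PWV, and Recovery 2 is called a data collection visit. Four measures in the power calculation also fit tonometry at all four visits. Section 6.2, Initial Visit, refers to Figure 1 for all time points, and that figure may settle what staff do. This objection stands against any claim of certain loss. It does not remove the conflict: even if Figure 1 lists tonometry at recovery, the Recovery 1 wording in 6.1 and 6.2 would still need correcting.

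A reader might also infer that the primary comparison is compromised. It is not. Aim 1 and the cf-PWV test in section 17.1 use measurements taken after each four-day intervention, and no aim, hypothesis or endpoint is framed around recovery.

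Nor do the mood data stand in the same position. Section 6.2 uses the mood questionnaire for shifts associated with the intervention and promises no three-day recovery value.

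Uneven collection is a risk, not a forecast. This is a single site, and section 25.0 provides for meetings with each team member about procedures. Finally, the sample size text does not say which four measures it means, so the link to the four visits is an inference, though the natural one.

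**Conclusion.** The contradiction is real and lies in the primary-outcome domain. Up to 2 of 4 cf-PWV and central blood pressure measurements per participant (at most 60 of 120 at 30 completers) are at risk of being missed or collected unevenly. Confidence that data would actually be lost is moderate, because other text supports collection and Figure 1 could not be read. The data for the normal versus restricted sleep comparison are unaffected.

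The power statement holds approximately if four cf-PWV values are taken and analysed. If only two enter the analysis, power at the plan's own f and correlation is about 0.61 at N = 24 and 0.72 at N = 30. That rests on f being the same for two and four measures, sphericity, and ρ = 0.5.

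This should be settled before recovery visits proceed, since a missed three-day value cannot be recovered.

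**What to change.** Reconcile section 6.1, section 6.2 (Experimental Visits and Central Hemodynamic Assessment) and Figure 1 in one of two ways:

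- List pulse wave analysis and cf-PWV at Recovery 1 and Recovery 2, in the same position as at the Post-Tests (before venipuncture and the jump test), and itemise Recovery 2; or
- Delete the three-day hemodynamic recovery purpose and make no claim about hemodynamic recovery.

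In either case, state in section 17.1 how many cf-PWV values per participant are taken and how many enter the analysis, and base the number of measures in the power calculation on that. If the test uses only the two Post-Test values, report the calculation for two measures.

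Cost: a wording amendment. The first option adds a short supine measurement at two visits participants already attend, with equipment on site. The second gives up the recovery question for this outcome. An analysis on two values also means a less favourable stated power.

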6.5 N/A

6.6 N/A

7.0 Data and Specimen Banking

7.1 Blood specimens will be kept in closed containers within the ISSM freezer (-80° C) behind two locked doors for batch analysis. After the analysis of the data, specimens will be maintained for 3 years. Data will be kept on password protected FSU computers or in physical copies behind locked drawers and doors in the PI's office. The verified research team are the only people who will have access to the data or specimens.

7.2 The information will be included in the data or associated with the specimens will be coded and unidentifiable without the code. The

code will be kept in physical copy behind two locked doors and a third locked drawer, or in electronic copies in a password protected file.

- 7.3 The PI will be responsible for receipt or transmission of the data or specimens until graduation. After such event, the co-investigator, [name], will be responsible for receipt or transmission of data or specimens.

7.4 N/A

8.0 Sharing of Results with Subjects

- 8.1 Individual subject results for anthropometric data will be provided upon the completion of the study protocol. The results will be shared exclusively with the individual via print or word of mouth.

9.0 Study Timelines

9.1 *Describe:*

- The duration of an individual subject's participation in the study is ~1.5 months (~35 days).
- The duration anticipated to enroll all study subjects is 18 weeks.
- The estimated date for the investigators to complete this study (complete primary analyses) is December 2025.

10.0 Inclusion and Exclusion Criteria

10.1 Eligibility.

Inclusion Criteria:

Men and women will be recruited to participate in this study. Inclusion criteria will be as follows:

- a) Age: 18-39 yrs
- b) Active (>150 minutes of aerobic exercise per week)
- c) Sedentary (<150 minutes of aerobic exercise per week)

Exclusion Criteria:

Participants will be excluded from participation in the study for the following reasons:

- a) Participants known to have chronic, uncontrolled metabolic, cardiovascular, or hepatic disease including:
 - a. Diagnosed cardiovascular diseases or previous myocardial infarction
 - b. Uncontrolled hypertension
 - c. Diabetes (Type 1 or 2)

d. Uncontrolled thyroid conditions

- b) Participants known to have injuries limiting exercise capacity
- c) Participants classified as grade III obese (BMI: ≥ 40 kg/m²)
- d) Participants known to be pregnant

10.2 N/A

10.3 None of the aforementioned special populations will be included in this research.

11.0 Vulnerable Populations

N/A

12.0 Local Number of Subjects

12.1 30

12.2 The PI anticipates <20% attrition in this population, therefore the PI plan to recruit no more than 36 participants to ensure a final number of 30 successfully complete the protocol.

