25.0 Resources Available

- Between various recruitment locations mentioned, we anticipate an ample amount (>50) of eligible subjects. As the power analysis revealed a required sample size of 30, the PI does not anticipate any issues regarding recruitment.
- The PI aims to complete data collection no later than Spring 2026 and complete data analysis and writing no later than Summer 2026.
- The ISSM is a well-funded, fully stocked human performance laboratory. It has all the equipment and space needed to fully support this research. The facilities are more than satisfactory for the completion of this study.
- First Aid, automated external defibrillator (AED), fire extinguishers, and showers are available at each location. All data collection visits will be attended by CPR-trained staff. Although unlikely, any medical needs beyond the scope of first aid will consist of a researcher escorting the participant to the FSU medical center on campus.
- The PI will have several meetings with each person in the research team going over each individual role. This will help ensure that each member of the research team is adequately informed about the protocol, the research procedures, and their duties and functions.

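### Sample-size figures conflict: 30 is the number recruited in Section 17.1, the number completing in Section 12.2 and the power-analysis result in Section 25

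*Combined protocol and SAP*

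**What the plan says.** **Section 17.1 (Sample Size Estimation).** The power calculation takes an effect size of f = 0.24, two groups measured four times, a within-person correlation of 0.5, 5% significance and 80% power. The result: "This resulted in a sample size estimate of 24 participants". The number is then raised for three reasons: differences from the earlier study, several secondary outcomes, and attrition of about 20%. The conclusion: "Therefore, 30 participants will be recruited to maximize statistical power and account for expected attrition". Here 30 is the number entering, with attrition included.

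**Section 12.2 (Local Number of Subjects).** Attrition is put below 20%, and the plan is to "recruit no more than 36 participants to ensure a final number of 30 successfully complete the protocol". Here 30 is the number finishing, with attrition added on top.

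**Section 25 (Resources Available).** "As the power analysis revealed a required sample size of 30". Here 30 is the output of the power analysis.

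Section 1 (Study Summary) and Section 12.1 give only the bare figure 30, so they do not settle which meaning applies.

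**The concern.** A sample-size statement should let a reader follow one chain: number required for power, number expected to complete, number to recruit. Here the chain breaks at each link. Someone following Section 17.1 stops recruiting at 30 and expects about 24 completers at 20% loss. Someone following Section 12.2 may go to 36 and expects about 29. Section 25 reports a required number that Section 17.1 contradicts.

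At stake are the enrolment stop, the sample-size rationale that will be reported, and whether any margin exists beyond attrition. If the text is left as it is, the stopping point can be chosen during recruitment and either choice can be defended from the protocol.

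**Working it through.** **1. Section 17.1: from 24 to 30.** Inputs: 24 required, attrition about 20%.

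- Recruits = n/(1 - d) = 24/0.80 = 30, which reproduces the plan's figure exactly.
- Attrition alone therefore accounts for all 6 added participants. Nothing remains for the differences from prior work or the secondary outcomes.

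**2. Section 12.2: from 30 to 36.** Inputs: 30 completers, at most 36 recruits, attrition below 20%.

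- 30 × 1.2 = 36 matches the plan's figure. The protocol shows no formula, so this match does not establish how 36 was obtained.
- n/(1 - d) at d = 0.20: 30/0.80 = 37.5, so 38.
- Attrition at which 36 gives an expected 30: 1 - 30/36 = 16.7%.

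Expected completers from 36, and the chance of at least 30 if losses are independent (binomial, n = 36):

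| Attrition | Expected completers | P(30 or more) |
|---|---|---|
| 10% | 32.4 | 0.94 |
| 15% | 30.6 | 0.71 |
| 16.7% | 30.0 | 0.61 |
| 19% | 29.2 | 0.46 |
| 20% | 28.8 | 0.40 |

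Attrition of 19% still satisfies the plan's own bound, yet 30 is then missed more often than not.

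**3. The power-analysis figure of 24.** Inputs from Section 17.1: f = 0.24, alpha = 0.05, k = 2 groups, m = 4 measures, r = 0.5. The test is the within-between interaction named under Analysis of Variance in the same section.

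- Noncentrality: λ = f² × N × m/(1 - r)
- Degrees of freedom: (k - 1)(m - 1) = 3 and (N - k)(m - 1)
- At N = 24: λ = 0.0576 × 24 × 4/0.5 = 11.06, df = 3 and 66, power 78.0%

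| N | Power |
|---|---|
| 24 | 78.0% |
| 26 | 81.7% |
| 29 | 86.3% |
| 30 | 87.6% |
| 36 | 93.4% |

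So 24 falls about two points short of the stated 80%, and 26 is the smallest number in equal groups that reaches it. Rounding of f could nearly explain the gap: f = 0.2449 also prints as 0.24 and gives 79.8% at N = 24.

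**4. The three roles of 30, side by side.**

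| Section | Required by power analysis | Recruited | Completers at 20% loss |
|---|---|---|---|
| 17.1 | 24 | 30 | 30 × 0.80 = 24 |
| 12.2 | not stated | up to 36 | 36 × 0.80 = 28.8 (30 claimed) |
| 25 | 30 | not stated | not stated |

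No single reading satisfies all three rows.

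**The case against.** The strongest defence is that the practical harm is small. Section 12.2 gives an upper bound on attrition, not a forecast of exactly 20%, so 28.8 is the boundary case. At 15% attrition, 36 recruits give 30.6. Even at 20% the shortfall is 30 - 28.8 = 1.2 completers, or 36 recruits where 38 would be derived. Going from 30 to 29 completers costs 87.6 - 86.3 = 1.3 points of power, and 36 recruits at 20% loss still leave at least 24 completers with probability about 0.98. Section 14.3 also allows data collected before withdrawal to be used, so the number analysed need not equal the number completing. All of this stands, and it limits the severity. It does not reconcile the three meanings of 30, and it does not support a claim that 36 ensures 30.

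A reader might also infer stronger points that the documents do not support:

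- **Power of only 61% at 24, 70% at 29 and 72% at 30.** These values come from two measures with f = 0.24. Section 17.1 specifies four. How many measures the primary comparison really has is a separate question, and the 24/30/36 conflict does not cause it.
- **The 24 is simply wrong, or was computed with f = 0.25.** The gap is at most two participants or two power points, and f of about 0.246 already reaches 80%.
- **Screen failures will use up the cap of 36.** Consent does precede the VO2max test (Section 6.2), but no section says the cap is counted at consent. Recruitment also targets active and sedentary people, not an unselected population. The counting rule needs stating, but no shortfall follows from the text.

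**Conclusion.** The concern holds as a should-fix inconsistency. Required N is 24 in Section 17.1 and 30 in Section 25. Recruitment is 30 with attrition included in Section 17.1 and up to 36 with attrition added in Section 12.2. Two further statements are not supported as written: that the step from 24 to 30 covers more than attrition, and that 36 recruits ensure 30 completers when attrition may be anything below 20%.

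The consequence for power is modest on the plan's own inputs. The only figure below the stated 80% is 78.0% at 24 completers, which is what Section 17.1's recruitment number yields at 20% loss. It would be tempting to call the trial underpowered or the arithmetic of Section 12.2 seriously wrong, but the documents support neither.

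The power values assume the stated f, four measures, r = 0.5, sphericity and the standard repeated-measures interaction formula. The completion probabilities assume independent losses at a common rate.

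**What to change.** - **One chain of numbers.** In Sections 1, 12, 17 and 25, give one completer target and one recruitment number derived as n/(1 - attrition). The target is the investigator's choice: 24 completers need 30 recruits at 20%, and 30 completers need 38. Alternatively, keep the cap of 36 and restate expected completers as about 29 at 20% attrition.
- **Wording of Section 12.2.** Replace the assurance of 30 completers with an expected number.
- **Power.** Quote it at the expected completer number: with the stated inputs, 78.0% at 24, 86.3% at 29 or 87.6% at 30. Report f to enough decimals that the base figure can be reproduced.
- **Section 25.** Say that the power analysis gave 24, or 26 if it is recomputed with f = 0.24.
- **Section 17.1.** If 30 remains the recruited number, drop the statement that the increase also covers differences from prior work and secondary outcomes.
- **Counting rule.** State that the cap counts participants who qualify after the VO2max test.

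The cost is mainly wording, best settled before enrolment closes. Keeping 30 completers as the target would mean raising the cap by two, from 36 to 38. The approved number of consents may also need to be higher to cover people who do not qualify.
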